For each cohort, a SRC meeting will be held after the end of the third subject's Cycle 2 of the preceding cohort and before the second administration of the first subject in a cohort, (Figure 2) to review all available safety data and radiation exposure from previous cohort(s). The second radioactivity administration will be confirmed based on the rules described in Attachment 5, Section 19.5.

Stopping Rules for Dose Escalation

The MTCA is defined in Section 4.2.1.1.

The radioactivity escalation will be stopped as soon as:

- The MTCA and/or MTSA have been defined with good precision; or
- The maximum planned radioactivity of 15 GBq, fractionated into two administrations separated by 4 weeks, is administered without safety concerns.

Transition from Dose Escalation to Other Study Parts

Upon completion of the phase I dose escalation or upon reaching the MTCA and confirmed jointly by the SRC and the sponsor, and in consideration of the accumulated subject data, cohorts of subjects will be studied to further characterise the safety and efficacy of ¹⁷⁷Lu-3BP-227. In the case of acceptable tolerability and evident antitumour activity across all enrolled subjects in phase I, a phase II basket trial design will be utilised to study the antitumour activity of ¹⁷⁷Lu-3BP-227 in subjects with NTSR1 expressing tumours. However, if the antitumour activity is driven by a certain type of tumour, tumour-specific phase II cohort(s) will be initiated utilising an Optimal Simon's Two Stage design (see Section 4.3).

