During the study, the target organ exposure will be monitored after each dose and doses may be adapted if the exposure exceeds organ-specific maximum acceptability limits. As such, if the predicted MTCA exceeds the maximum acceptability limits for target organ exposure, the maximum radioactivity dose will be used instead. This feature was not considered in the simulation study, where it was assumed that a cumulative dose up to 15 GBq would induce an acceptable organ exposure.

Prior distributions were elicited based on historical knowledge about the placebo DLT rate and the MTSA target. The following prior distributions are used in the trial:

$$p_0 \sim beta(a=1,b=9)$$
,
MTSA $\sim gamma$ (shape = 4, rate = 0.5),
and

 $\beta \sim normal \ (\mu = 0, sd = 0.25).$

Based on these distributions, 20 dose-DLT curves from the prior distribution were simulated after Dose 1 (black) and after Dose 1 and 2 (red) (see Figure 3). The prior probability distributions for the MTSA is summarised in Table 10. The prior probability distributions for the MTCA is summarised in Table 11

[figure not shown]

Figure 3 40 Random Observations (Curves) from the Prior Distribution

Table 10 Prior Probability Distribution of MTSA

Dose range for Cycle 1	Prior MTSA probability
2.5 GBq	5.2%
2.5 to 5 GBq	20.6%
5 to 7.5 GBq	28.6%
>7.5 GBq	45.6%

MTSA=Maximum tolerated single activity.

Table 11 Prior Probability Distribution of MTCA

Dose range (cumulative)	Prior MTCA probability
≤5 GBq	32.5%
5 to 10 GBq	24.6%
10 to 15 GBq	15.7%
>15 GBq	27.2%

MTCA= Maximum tolerated cumulative activity.

Given any set of data, the prior distribution can be updated, yielding a posterior distribution of the parameters. From this posterior distribution many different quantities of relevance can be calculated:

- $E(p|d_1, d_2)$ =Posterior mean probability of DLT for Cycle 1 dose d_1 and Cycle 2 dose d_2 .
- TS_d=(tolerable) Probability that the DLT rate is below 0.33, $Pr(p \le 0.33 | d,0)$, for a Cycle 1 dose d (d₂=0).
- QS_d=Probability of Cycle 1 dose d being the maximum dose where $E(p|d,0) \le 0.33$.
- TC_d=(tolerable) Probability that the DLT rate is below 0.33, $Pr(p \le 0.33 | d/2,d/2)$, for a cumulative dose d (d₁=d₂=d/2).
- QC_d=Probability of cumulative dose d being the maximum dose where E(p|d/2,d/2) <0.33.

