 - (a) if there are two DLTs out of three, three DLTs out of five, or three DTLs out of six subjects receiving a single or cumulative dose, d must be lower than or equal to that dose;
 - (b) if there are three DLTs out of three, or at least three DLTs out of four, or at least four DLTs out of five, or at least four DLTs out of six subjects receiving a single or cumulative dose, d must be lower than that dose;
 - (c) dose d must be at most 1 GBq larger than the maximum Cycle 1 dose tested previously.

Repeat steps 2 and 3 again, assigning the subjects/cohort to this dose. Terminate study enrolment when any of the following stopping rules happen:

- A the MTSA is precisely estimated: CV (MTSA) calculated as the inter-quartile range over the median is lower than 30%;
- B maximum possible dose (7.5 GBq) is safe: TS_{7.5}>80% and d₁=7.5 GBq administered;
- C minimum dose tested (2.5 GBq) is toxic: TS_{2.5} <20%;
- D total sample size for next dose is already ≥ 6 .

The MTSA will be declared to be found when study stops for criteria A or D.

Individual dosing decision for the second treatment cycle will be done as follows:

- Subject will be eligible for Cycle 2 only if subject had no DLT during Cycle 1. Subjects with DLTs in Cycle 1 will be discontinued and replaced with a maximum of two replacements.
- The same fractional dose as in Cycle 1 will be repeated during Cycle 2 ($d_2=d_1$), if the dose having the largest probability to be the MTCA is larger than 2 x d_1 .
- The fractional dose for Cycle 2 will be decreased to d₂=MTCA-d₁ dose, if the predicted cumulative exposure after Cycle 2 is above the MTCA target. In this situation, the cumulative exposure after two cycles should not exceed the MTCA.

The study will be terminated when all cohorts have ended the study, as defined above.

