19.5.5 Simulation Results

The operational characteristics for the five trial simulation scenarios are presented in Table 13. The mean (SD) sample size per dose is shown in Figure 5.

A box plot of the total sample size is in Figure 6 for Cohort 1 and in

Figure 8 for Cohort 2.

The number of cohorts is in

Figure 8

Overall, simulations performed as expected, under all scenarios, taking into account the constraints about the maximum fold-increase, the repeated dosing, the overdose control and the maximum sample size. The dose escalation for Cycle 1 was pursued up to the top single dose of 7.5 GBq under a similar pattern for the Safe, Early and Late scenarios, where the MTSA was either above the top dose (Safe, Late) or close to it (Early). Under the Toxic scenario, only low doses were administered, with an MTSA estimated near the first single dose (2.5 GBq) in most trials. When the MTSA and MTCA were within the dosage range (Peak), the escalation was performed up to the target dose of 5 to 5.5 GBq, followed by an adaptation around it. The MTSA and MTCA were found with precision in most trials and their relative errors remain good. There was a high proportion of trials stopped with the MTSA found (either based on CV or sample size criteria). As expected, sample size and cohort size were larger when escalation had to proceed up to the top doses (Safe, Late, Early) than when the MTSA was low (Toxic and Peak). In 80% of trial simulations, the total number of subjects was not larger than 28 in a maximum of seven cohorts. The number of overdoses was low in Cycle 1. It did not increase during Cycle 2, except when the second dose brought more toxicity (Early, Peak).

These results validate the use of the Bayesian model and the adaptive dose escalation plan for this study.

Table 13 Main Operational Characteristics for the Five Trial Simulation Scenarios

Criterion	A: Safe	B: Late	C: Early	D: Toxic	E: Peak
% stops for reason: 2.5 GBq is toxic				23.4	
% stops for reason: 7.5 GBq is safe	58.9	46.4	5.90		
% stops for reason: CV (MTSA) \le 30%	34.0	42.4	69.0	34.1	92.1
% stops for reason: N≥6	7.10	11.2	25.1	42.5	7.90
% trials (MTSA>top dose)	94.9	92.5	48.8		0.8
% trials (MTSA <first dose)<="" td="">			38.1		</first>				38.1	
Median MTSA (GBq)	10.5	9.9	7.4	2.7	4.8
Median MTSA Rel. Error (%) [a]	30.2%	29.2%	15.3%	34.2%	13.8%
Mean CV (MTSA) (%)	28.8%	28.9%	28.9%	43.5%	21.5%
Median MTCA (GBq)	17.4	14.7	9.5	4.2	6.2

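### Stopping rule A (IQR/median of the MTSA below 30%) does not produce the precision-stop shares and CV values printed in Table 13 for the Safe, Late and Early scenarios

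*Protocol*

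**What the plan says.** Section 4.2.1.4 of the protocol stops escalation when "The MTCA and/or MTSA have been defined with good precision", with no threshold. The only numerical meaning of precision is rule A in 19.5.2: "CV (MTSA) calculated as the inter-quartile range over the median is lower than 30" per cent. The formula has no scaling constant. The other stops are B ("maximum possible dose (7.5 GBq) is safe", posterior probability above 80%, with 7.5 GBq administered), C ("minimum dose tested (2.5 GBq) is toxic", probability below 20%) and D ("total sample size for next dose is already ≥ 6"). A stop on A or D counts as having found the MTSA.

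Table 13 in 19.5.5 reports the share of 1,000 simulated trials stopped by each rule. Precision stops are 34.0% (Safe), 42.4% (Late), 69.0% (Early), 34.1% (Toxic) and 92.1% (Peak). Mean CV(MTSA) is 28.8, 28.9, 28.9, 43.5 and 21.5%. The only formula under the table defines relative error, and no second definition of CV appears. From these results 19.5.5 concludes that the model and escalation plan are validated and states: "In 80% of trial simulations, the total number of subjects was not larger than 28 in a maximum of seven cohorts". Section 12.2.1.1, and SAP 1.3.4 after it, refer to the simulations for precision and sample size.

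**The concern.** A posterior IQR below 30% of the median is a demanding target for a trial of about 15 to 20 subjects with few DLTs. A mean CV of about 29% in scenarios where most subjects have no DLT looks too small to be an IQR/median. If the tabulated CV is on another scale, rule A and Table 13 describe different stopping criteria. A statistician applying 19.5.2 literally would run a rule whose stop behaviour is not reported. A team relying on Table 13 would believe that precision had been reached at an IQR of 30% of the median, when the simulated trials stopped at roughly 40%.

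**Working it through.** **Inputs (protocol 19.5.1 to 19.5.4).** Model: logit p = logit p0 + (logit 0.33 − logit p0) × d1/MTSA + β × d2. Priors: p0 ~ Beta(1, 9), MTSA ~ Gamma ("shape = 4, rate = 0.5"), β ~ Normal(0, SD 0.25). Planned steps are 2.5, 4, 5.5, 6.5 and 7.5 GBq per cycle, three subjects per cohort, with at most two replacements. True DLT rates are those of Table 12.

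**1. Is this the model that was used?** The stated priors give MTCA bands of 31.6/25.8/15.7/27.0% against 32.5/24.6/15.7/27.2% in Table 11 (negative values counted in the lowest band). They give MTSA bands of 3.8/20.4/27.4/48.4% against 5.2/20.6/28.6/45.6% in Table 10. The agreement is close, though not exact.

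**2. Starting point.** The prior MTSA quartiles are 5.07, 7.34 and 10.22, so IQR/median = (10.22 − 5.07)/7.34 = 0.70. The data must more than halve this ratio to reach 0.30.

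**3. Fixed data.** Take five cohorts of three and no DLT, using Cycle 1 only. The posterior quartiles are 9.86, 11.98 and 14.69.
- IQR/median = 4.83/11.98 = 0.403
- IQR/(1.349 × median) = 0.403/1.349 = 0.299
- SD/mean = 0.304

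Adding DLT-free Cycle 2 data gives 0.384 and 0.285 for the first two. Across patterns of 0 to 3 Cycle 1 DLTs, IQR/median lies between 0.36 and 0.44. No pattern falls below 0.30.

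**4. Full re-simulation.** Escalation, replacement, Cycle 2 dosing and stops A to D were simulated with 1,000 trials per scenario in the main reconstructions. What the text leaves open was varied: likelihood coding of the two cycles, conditional or independent Cycle 2 DLTs, escalation trigger, order of stop checks, and Monte Carlo noise down to 200 effective draws.

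| | Safe | Late | Early |
|---|---|---|---|
| Printed precision stops, % | 34.0 | 42.4 | 69.0 |
| Written rule, main reconstructions, % | 0.1–2.8 | 1.0–4.1 | 23–37 |
| Written rule, highest in any variant, % | 10 | 10 | 47 |
| IQR/(1.349 × median) < 30%, % | 40–77 | 45–68 | 59–79 |
| Printed mean CV(MTSA), % | 28.8 | 28.9 | 28.9 |
| Mean IQR/median, written rule, three main runs, % | 39.6–41.7 | 39.8–41.0 | 36.5–37.8 |
| The same divided by 1.349, % | 29.4–30.9 | 29.5–30.4 | 27.1–28.0 |

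Over all reconstructions the mean IQR/median in these scenarios is about 34 to 42%. The standard error of a printed share is about 1.5 points (√(0.34 × 0.66/1000) = 0.015), so simulation noise does not explain the gap. Under the written rule the missing precision stops mostly become rule B stops: 87 to 96% in Safe and 72 to 84% in Late, against 58.9% and 46.4% printed.

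**5. Size of the rescaling.** 1/1.349 = 0.74, so the scaled CV is about a quarter smaller. A scaled threshold of 30% corresponds to IQR/median of 0.30 × 1.349 = 0.405. SD/mean gave precision stops of 22 to 39% in Safe and 25 to 40% in Late, depending on the variant, with mean CV of about 31 to 32% where recorded.

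**6. Sample size.** Mean Cycle 1 N, written against scaled rule, within the same reconstruction:
- Safe: 16.5 v 16.2, 18.4 v 18.2, 18.9 v 18.3 (printed 17.5)
- Late: 17.6 v 17.1, 19.2 v 18.6, 19.4 v 18.7 (printed 17.7)
- Early: 22.7 v 20.0, 24.1 v 20.5, 24.4 v 21.8 (printed 18.7)

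**The case against.** **The reconstruction is not the sponsor's program.** This stands as a limit. No candidate formula reproduces the exact split between rules A and B. The scaled CV with no DLT in 15 subjects (0.299) sits on the 30% line, so coding details and the noise of a single 1,000-iteration chain would decide many stops. The printed mean CV(MTCA) of 17.3% in Safe was not reproduced either. The conclusion about the written rule is sturdier than this, because no variant brought it near the printed shares.

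**A reader might infer that the simulation is shown to have used IQR/(1.349 × median).** The documents do not support this. They contain neither a rescaled IQR nor the code, and SD/mean is also close to 0.30.

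**A reader might infer that the printed sample sizes, or the 28-subject sentence, belong to another design.** That is too strong. Setting a re-simulated Early mean of about 24 against the printed 18.7 mixes two gaps, since the scaled rule itself gives 20 to 22 in the main runs. The rule accounts for about two to four subjects. Under the written rule the 80th percentile of Cycle 1 N is 15 to 23 in four scenarios and 29 to 30 in Early (28 with the scaled rule). Section 19.5.5 does not say whether its 80% is pooled or per scenario.

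**A reader might take Toxic and Peak as further evidence.** They do not discriminate. In Peak the written rule gives anything from 47 to 98% precision stops depending on coding choices that the text does not fix. The Toxic mean CV is just as sensitive.

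**Rule A has limited operational weight.** It appears under simulation details, modelling at committee meetings is optional, and the safety review committee decides with the sponsor. That lowers the stakes. It remains the only number attached to precision in the protocol, and the basis on which the plan is called validated.

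**Conclusion.** The point holds for the stop reasons and the CV rows. With the stated model, priors and Table 12 truths, rule A as written cannot yield the precision-stop shares or mean CV(MTSA) printed for Safe, Late and Early. The shortfall is about 30 percentage points or more in Safe and Late and roughly 30 to 45 in Early in the main reconstructions. It remains at least 20 points in every variant tried. The likely explanation is a CV about a quarter smaller than IQR/median, but which formula was coded is an inference. Mean sample size changes by less than one subject in Safe and Late and by about two to four in Early. Nothing here shows that the planned number of subjects is wrong. The conclusion assumes that the priors and likelihood in 19.5.1 are those simulated, which Tables 10 and 11 broadly support.

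**What to change.** Check the simulation code and state the CV formula actually used, in rule A of 19.5.2 and in the label of the Table 13 CV rows. Then make text and table agree in one of two ways:

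- If the code used a scaled IQR, SD/mean or another quantity, rewrite rule A with that formula. If it proves to be IQR/(1.349 × median), say that 30% then means an IQR of about 40% of the median.
- If unscaled IQR/median below 30% is intended, re-run the simulations, replace Table 13 and Figures 5 to 8, and re-check the 28-subject, seven-cohort sentence in 19.5.5.

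In either case, cross-refer the resulting criterion from 4.2.1.4 so that good precision has a stated meaning there. The cost is a line or two of protocol text, or a re-run of existing code. After a re-run, the precision-stop shares would fall and the Early sample size would probably rise slightly.

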19.5.1 Statistical Model

After study screening procedures, eligible subjects will receive up to 2 i.v. administrations of 177 Lu-3BP-227 in two consecutive treatment cycles 4 weeks apart. A range of doses will be tested, including possibly 2.5, 3, 3.5, 4, 4.5, 5, 5.5, 6, 6.5, 7 and 7.5 GBq per cycle. Additional or alternative dose levels may be chosen. These possible dose levels are labelled as d=1, ..., N, where N is the maximum number of dose levels for the study.

The analysis is based on a method reported by Guede et al.[9] and Tibaldi et al. [37].

If, during Cycle 1, a subject receives dose d_1 and in Cycle 2 dose d_2 , the probability, p, of observing a subject with DLTs up to 4 weeks after the two cycles of dosing is modelled as a function of dose as:

logit
$$(p) = \text{logit } (p_0) + \frac{\text{logit } (33\%) - \text{logit } (p_0)}{MTSA} d_1 + \beta * d_2$$

where p_0 , MTSA and β are the model parameters having the following interpretation:

- p_0 is the probability of observing DLTs under placebo ($d_1=d_2=0$),
- MTSA is the maximum tolerated single activity, being defined as the dose d₁ at which the predicted probability of DLTs is 33% for dosing Cycle 1 (single dose), and
- β is a slope coefficient indicating the impact of a second dose d_2 on DLT probability.

The prior distribution on p_0 , MTSA and β determine the prior distribution on the probability of DLT as a function of up to two doses. For cycle 1 data analysis, the dose d_2 is set to zero. So, only parameters p_0 and MTSA are involved. β is involved when subjects undergo their second cycle. A positive β indicates an increase in DLT probability with second dose.

The MTCA is defined as the maximum tolerated cumulative activity $(d=d_1+d_2)$, where $d_1=d_2$) that may be administered following fractionated i.v. administrations of the same dose d_1 at least 4 weeks apart so that no more than 33% of the subjects experience a DLT during Cycles 1 and/or 2.

The MTCA can be presented as a derived parameter from the logistic regression model. It is expressed as:

$$MTCA = 2* MTSA * \frac{\text{logit } 33\% - logit }{\text{logit } 33\% - \text{logit } p_0 + \beta * MTSA}.$$

The MTCA will be equal to twice the MTSA when β equals 0 (i.e. the DLT probability is not changed after a second dose). When the DLT probability is increased (β >0), the MTCA will be decreased (and vice versa).

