19.5.3 Simulation Scenarios

Five dose-DLT profiles were considered to evaluate the operational characteristics of the adaptive dose escalation trial (see Figure 4 and Table 12 below). The five scenarios are:

Scenario A – Maximum dose safe: This scenario represents a negative scenario under which all doses are safe for the two dosing occasions. The true MTSA (15 GBq) and true MTCA (30 GBq) are larger than the maximum possible doses in the study.

Scenario B - Late MTCA: This is a scenario is which the MTCA=MTSA=14 GBq. All Cycle 1 doses are safe. After Cycle 2, cumulative doses up to and including 14 GBq are safe. The probability of a DLT is gradually increasing across all dose levels.

Scenario C – **Early MTCA:** In this scenario, the rate of DLT progression is faster over doses so that the MTSA (7 GBq) during Cycle 1 appears near the end of the dosage range. The MTCA after Cycle 2 is 9 GBq.

Scenario D - Toxic: Under this scenario, all doses are toxic, with a DLT rate of 46% at the lowest single dose of 2.5 GBq or at the repeated cumulative dose of 5 GBq. The MTSA (2 GBq) is below but close to the lowest single dose of 2.5 GBq. The MTCA is also equal to 2 GBq, so that any Cycle 2 dosing is toxic.

Scenario E - Peak: In this scenario, there is a step function in the probability of DLTs occurring in the middle of the dose escalation process during Cycle 1 and early in Cycle 2. The first doses up to and including MTSA=5.5 GBq are very safe (p=5%), and all subsequent single doses are toxic (p=80%). After Cycle 2, the MTCA is 5 GBq and all subsequent doses are toxic.

[figure not shown]

Figure 4 Dose versus DLT Rates After Cycle 1 and Cycle 2 Simulation Scenarios

Table 12 Simulated Dose-DLT Probabilities

Dose (GBq)	A: Safe	B: Late MTD	C: Early MTD	D: Toxic	E: Peak
Cycle 1					
2.5	7%	7%	10%	46%	5%
3.0	8%	8%	12%	60%	5%
3.5	8%	8%	14%	72%	5%
4.0	9%	9%	16%	82%	5%
4.5	9%	10%	18%	89%	5%
5.0	10%	10%	21%	93%	5%
5.5	11%	11%	23%	96%	5%
6.0	11%	12%	26%	98%	80%
6.5	12%	13%	30%	99%	80%
7.0	13%	14%	33%	99%	80%
7.5	14%	15%	37%	100%	80%
Cycle 2			•		
5.0	7%	10%	15%	46%	5%
6.0	8%	12%	18%	60%	80%
7.0	8%	13%	21%	72%	80%
8.0	9%	15%	26%	82%	80%
9.0	9%	17%	30%	89%	80%
10.0	10%	20%	36%	93%	80%
11.0	11%	22%	41%	96%	80%
12.0	11%	25%	47%	98%	80%
13.0	12%	28%	53%	99%	80%
14.0	13%	32%	58%	99%	80%
15.0	14%	35%	64%	100%	80%

DLT=dose limiting toxicity, MTD=maximum tolerated dose.

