19.5.4 Operational Characteristics

We used 1000 trial simulations to monitor the following properties of the adaptive design under the five scenarios:

- accuracy and precision of the MTSA and MTCA
- probability of archiving each of the four stopping rules (MTSA precision, last dose is safe, first dose is toxic, maximum sample size)
- total sample size after Cycle 1 and Cycle 2

- total number of cohorts
- number and proportion of subjects being overdosed during Cycle 1 and Cycle 2 (i.e. relative to the true MTSA and MTCA, respectively)
- subject distribution across dose levels.

Calculations were performed in R statistical software version 2.7.2 and using the BRugs package running on OpenBUGS version 2.2.0 for the Bayesian estimation. The posterior distribution was estimated using one MCMC chain based on 1000 iterations, after a burn-in of 2000 samples. The initial values were set to p_0 =5%, MTD=5 GBq and β =0. Convergence was monitored by visual inspection of the diagnosis plots for a sample dataset spread across all five scenarios.

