Median MTCA Rel. Error (%) [a]	41.9%	19.7%	16.9%	112%	25.2%
Mean CV (MTCA) (%)	17.3%	26.9%	39.5%	54.2%	25.7%
Mean (SD) number of overdosed subjects (Cycle	0.0(0.0)	0.0(0.0)	1.8 (2.1)	9.1 (3.6)	5.5 (1.5)
1)					
[Min, Max]	[0.0, 0.0]	[0.0, 0.0]	[0.0, 5.0]	[5.0, 19.0]	[0.0, 14.0]
Mean (SD) number of overdosed subjects (Cycle	0.0(0.0)	1.7 (1.5)	6.3 (2.9)	3.6 (1.9)	7.8 (1.9)
2)					
[Min, Max]	[0.0, 0.0]	[0.0, 3.0]	[0.0, 12.0]	[0.0, 9.0]	[0.0, 15.0]
Mean (SD) number of subjects (Cycle 1)	17.5 (3.0)	17.7 (3.3)	18.7 (4.3)	9.1 (3.6)	15.9 (2.5)
[Min, Max]	[5.0, 25.0]	[5.0, 28.0]	[5.0, 31.0]	[5.0, 19.0]	[5.0, 28.0]
Mean (SD) number of subjects (Cycle 2)	15.7 (2.5)	15.7 (2.7)	14.3 (3.3)	3.6 (1.9)	10.8 (2.0)
[Min, Max]	[2.0, 21.0]	[2.0, 21.0]	[2.0, 21.0]	[0.0, 9.0]	[2.0, 18.0]
Mean (SD) number of cohorts	5.3 (0.8)	5.3 (0.9)	5.1 (1.1)	2.0 (0.9)	4.4 (0.6)
[Min, Max]	[1.0, 7.0]	[1.0, 7.0]	[1.0, 7.0]	[1.0, 4.0]	[1.0, 7.0]

CV=coefficient of variation; Max=maximum; Min=minimum; MTSA=maximum tolerated single activity.

a Rel. Error=|MTD_{true}-MTD_{median}|/MTD_{true}

[figure not shown]

Figure 5 Mean (SD) Sample Size per Single or Cumulative Dose Level for the Five Simulation Scenarios

[figure not shown]
[figure not shown]

Figure 6 Boxplot of Total Number of Subjects During Cycle 1 for the Five Simulation Scenarios

Figure 7 Boxplot of Total Number of Subjects During Cycle 2 for the Five Simulation Scenarios

[figure not shown]

Figure 8 Boxplot of Total Number of Cohorts for the Five Simulation Scenarios

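### The Cycle 2 reduction rule caps unequal fractions at an MTCA derived for equal fractions, so a pair at the cap can exceed the 33% cumulative DLT limit (Scenario C: 34.0% at 5.5+3.5 GBq, 37.9% at 6.5+2.5 GBq)

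*Protocol*

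**What the plan says.** Protocol 19.5.1 models the DLT probability over both cycles with one slope for the first dose and another for the second; beta "is a slope coefficient indicating the impact of a second dose". It defines the MTCA for two administrations of the same dose, "so that no more than 33% of the subjects experience a DLT during Cycles 1 and/or 2", and the closed-form MTCA expression rests on d1 = d2.

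Protocol 19.5.2 gives the individual Cycle 2 rule. A subject without a Cycle 1 DLT repeats d1 if the most probable MTCA is larger than twice d1. The second dose is reduced to MTCA − d1 "if the predicted cumulative exposure after Cycle 2 is above the MTCA target".

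This rule is not confined to the simulations. Protocol 4.2.1.4 states: "The second radioactivity administration will be confirmed based on the rules described in Attachment 5, Section 19.5". SAP 3.2.25 describes the SRC's role and possible use of the model, but gives no separate Cycle 2 dosing rule.

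The simulations (19.5.4) report the "number and proportion of subjects being overdosed during Cycle 1 and Cycle 2 (i.e. relative to the true MTSA and MTCA, respectively"). Cycle 2 overdosing is therefore judged by total activity.

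**The concern.** The reduction always produces an unequal pair with d1 above half the MTCA. The equal-fraction MTCA bounds the risk of such a pair only if a GBq given in Cycle 2 carries at least as much risk as a GBq given in Cycle 1. If the first-dose slope is steeper, moving activity into Cycle 1 at a fixed total raises cumulative risk, and a pair that satisfies the cap can break the 33% limit behind it. Nothing in the rule checks the predicted risk of the pair actually given, although 19.5.1 already defines the quantity needed ("Posterior mean probability of DLT for Cycle 1 dose" d1 and Cycle 2 dose d2). Such subjects would also not count as overdosed in Table 13.

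**Working it through.** **Inputs.** Model and MTCA formula: 19.5.1. Scenario C: MTSA 7 GBq and, from 19.5.3, "The MTCA after Cycle 2 is 9 GBq". Listed doses: 2.5 to 7.5 GBq per cycle in 0.5 GBq steps (19.5.1). The scenario's p0 and beta are not stated; p0 = 5% and beta = 0.15 are inferred from Table 12.

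**Model.** logit p = logit p0 + a·d1 + beta·d2, with a = (logit 33% − logit p0)/MTSA = (−0.7082 + 2.9444)/7 = 0.3195 per GBq.

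**Reproducing the plan.** These values return all 22 Scenario C entries of Table 12 after rounding (Cycle 1: 10% at 2.5 to 37% at 7.5 GBq; both cycles: 15% at 5 to 64% at 15 GBq). The MTCA formula gives 2 × 7 × 2.2363/(2.2363 + 0.15 × 7) = 9.53 GBq. The stated 9 GBq is thus the largest whole-GBq total at or below 33% (30% at 9, 36% at 10).

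**Direction.** At a fixed total T, logit p = logit p0 + beta·T + (a − beta)·d1. Risk rises with d1 when beta < a, is unchanged when they are equal, and falls when beta > a. In Scenario C beta is about half of a.

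**Size at the 9 GBq cap.** For 5.5+3.5: −2.9444 + 1.7571 + 0.5250 = −0.6624, which is 34.0%. For 6.5+2.5: −2.9444 + 2.0765 + 0.3750 = −0.4929, which is 37.9%. Conditional Cycle 2 risk is (p12 − p1)/(1 − p1), where p1 is the risk after Cycle 1 and p12 the cumulative risk. The d2 that meets 33% exactly is (2.2363 − a·d1)/beta.

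| d1+d2 (GBq) | Risk after Cycle 1 | Cumulative risk | Cycle 2 risk given no Cycle 1 DLT | Cumulative risk if d1 is repeated | d2 giving 33% (GBq) |
|---|---|---|---|---|---|
| 4.5+4.5 | 18.14% | 30.33% | 14.9% | 30.3% | 5.32 |
| 5+4 | 20.63% | 32.15% | 14.5% | 35.5% | 4.26 |
| 5.5+3.5 | 23.37% | 34.02% | 13.9% | 41.0% | 3.19 |
| 6+3 | 26.35% | 35.95% | 13.0% | 46.8% | 2.13 |
| 6.5+2.5 | 29.57% | 37.92% | 11.9% | 52.7% | 1.06 |

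From d1 = 7 the rule's d2 falls below the lowest listed dose, so nothing is claimed there. With the unrounded 9.53 GBq cap, the risks at d1 = 5.5 and 6.5 are 35.8% and 39.8%.

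**Listed doses that comply.** 5.5+3.0 gives 32.4%. At d1 = 6 the smallest listed second dose, 2.5, gives 34.2%, so no listed dose qualifies at 6 or above.

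**Scenario B.** p0 = 5%, MTSA = 14 and beta = 0.15 give a = 2.2363/14 = 0.160, almost equal to beta. At the 14 GBq cap, 7+7 gives 31.5% and 7.5+6.5 gives 31.6%: neutral.

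**How many subjects.** An approximate re-simulation of Scenario C used the stated priors and rules, three readings of how the MTCA estimate is taken, and two seeds of 300 trials for each reading. Subjects above 33% risk but at or below 9 GBq in total numbered 0.04–0.05, 0.10–0.16 and 0.26–0.38 per trial for the three readings, in 2–9% of trials. It does not match Table 13 exactly (Cycle 2 subjects 17–18 against 14.3; overdosed 6.5–7.1 against 6.3), so it gives an order of magnitude only.

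**The case against.** The strongest reply is that the excess comes from d1, which a Cycle 2 rule cannot undo. Only subjects without a Cycle 1 DLT receive a second dose, and their Cycle 2 risk falls from 14.9% at 4.5+4.5 to 11.9% at 6.5+2.5. Escalation itself steers towards the MTSA, because 19.5.2 picks the next dose by its probability of being the maximum at 33% after Cycle 1 alone. At 7 GBq in Scenario C no positive second dose keeps cumulative risk within 33%. A total-activity cap also has its own rationale: the MTCA definition in 4.2.1.1 includes a cumulative organ-radiation criterion. The gap between the rule's d2 and the risk-matched d2 (0.3 to 1.4 GBq) is small beside the uncertainty in the MTCA, with a mean CV of 39.5% in Scenario C (Table 13). The model enters only once DLTs are reported (4.2.1.3), and the SRC makes the final decision (12.2.8).

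All of this stands, and it limits the size of the problem. It does not remove the mismatch: the plan states its limit as cumulative risk, and the rule the SRC is told to confirm against does not evaluate that risk for the pair given.

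Three stronger readings are tempting but unsupported. A reader might take 37.9% as the hazard of the second dose; most of it was incurred in Cycle 1. A reader might infer that Table 13 hides many overdoses; it already reports 6.3 of 14.3 Cycle 2 subjects in Scenario C, its metric is openly defined, and re-scoring would change that count little. A reader might conclude that 33% must be a hard ceiling for every pair; that would force withholding at the doses the escalation seeks, which is a debatable trade-off and not a correction.

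**Conclusion.** The rule is wrong as written, with minor consequences. Applying an equal-fraction MTCA as a total cap allows a pair at the cap to exceed the 33% limit when beta is below the first-dose slope and d1 is above half the MTCA. In Scenario C the excess is 1.0 point at 5.5+3.5 and 4.9 points at 6.5+2.5; 5+4 stays within the limit because the stated 9 GBq is rounded down. The effect is quantified in one of five scenarios and is absent in Scenario B. In Scenario C the rule still lowers risk compared with repeating d1.

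The figures assume the inferred p0 and beta, and a cap equal to the scenario's stated MTCA; the trial would use an estimate. The number of subjects affected is likely well below one per trial.

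**What to change.** When the reduction applies, compute E(p|d1,d2) for the actual pair. Keep MTCA − d1 as the total cap. Where a listed d2 with E(p|d1,d2) ≤ 33% exists, use the largest such dose within the cap; in Scenario C, d1 = 5.5 would be followed by 3.0 GBq instead of 3.5 GBq.

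Where no listed d2 qualifies, which includes d1 near the MTSA, give the SRC the pair's predicted cumulative risk and its Cycle 2 risk given no Cycle 1 DLT. Let it choose the dose, with no automatic withholding. Re-scoring Cycle 2 overdoses in Table 13 by predicted risk is optional.

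The cost is one extra check on an output the attachment already defines, and an occasional smaller second dose.
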